Protocol for Sample Size / **Power calculations for surveys:** Simulations were run to determine the achieved power of our multiple baseline design resulting in an average of 240 participants per site for surveys collected at the beginning and end of four academic semesters at UHM and UHH and five academic semesters for HPU (20 data points, total n = 4,800). We assigned 60% of the students at baseline to already be a DOD (prior to being exposed to the intervention), based on the proportion we observed in previous work. Using an α =0.05 (two-sided) and a power of 80%, a simulation of 500 iterations found that the minimum detectable difference (MDD) in DOD prevalences comparing the 9 pre- and 11 post- intervention assessments, using our analysis approach, was 4 percentage points for an average change overall (3 campuses) and was 7 percentage points within a single campus; this was true assuming no change or a 3 percentage point drift in the pre-intervention prevalences over time.

Protocol for recruiting students for Study Surveys and Intervention activities Before taking the iDecide survey, students had to confirm they had read the consent form and actively consent (click yes). Eligibility was the verified. Only undergraduates enrolled at the three participating universities (UHM, UHH, HPU) were eligible, with enrollment verified by the respective university. Age was the only other eligibility criteria (18 years or older). Of the 8,001 online

consent forms completed, 853 (10.7%) reported enrollment at a nonparticipating university, and 2,073 (25.9%) didn't finish the survey. After verifying enrollment status for the remaining 5,075 survey entries, 248 (4.9%) were excluded because the student was not currently enrolled or was a graduate student, or their survey was a duplicate within that assessment; 4,837 was the final count.

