I'll do it if YOU do it first! Be an advocate, tell someone you know THEY can save 8 lives and improve the quality for up to 20 more, just by being an organ donor. Spread the word!	Sp2016	Sp2016	

4) Statistical Analyses Protocols

Two types of data sets would be created: a cross-sectional set and a longitudinal set. The cross-sectional dataset would include data from all surveys at each of the 20 assessment points (see Figure 1). The design allowed for students

to complete surveys at more than one assessment point. Due to uniqueness of student email addresses, those with repeat surveys could be identified. Thus, students could complete one or more pre-intervention surveys, one or more post-intervention surveys, or complete both pre and post-intervention surveys. The longitudinal dataset would include only those students who completed one or more baseline surveys and one or more post-test surveys.

The primary hypothesis was that exposure to the intervention would increase the percentage of students who reported being DODs on license and/or who spoke to their parents about their choice to be (or not be) a DOD on their license, and exposure would also improve knowledge and attitudes about OD. The primary analysis of the cross-sectional data used a logistic model of the outcomes DOD status or "talk to parents" regressed on a set of indicator variables reflecting each of the 20 assessment points (time by school combinations), adjusted for student's age, sex, race, and religion. Predicted DOD status (or family talk status) was computed from the model for each assessment point and the predicted statuses were compared between pre-intervention and post-intervention assessments using a t-test to test the primary hypothesis. We also repeated the test within subgroups defined by school and by covariates, such as race, to determine if the intervention effect differed by subgroups. Linear models regressing knowledge and attitude scores on assessment indicator variables and adjustment factors were used to determine the intervention effect on these scores.

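### The primary pre/post t-test pools assessments over three campuses without contrasting within campus, so residual campus differences can enter the estimate

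*Combined protocol and SAP*

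**What the plan says.** Under *4) Statistical Analyses Protocols*, a logistic model is fitted with one indicator per assessment, adjusted for age, sex, race and religion. Predictions are made at assessment level: each one "was computed from the model for each assessment point". The plan describes the test that follows in these words: "the predicted statuses were compared between pre-intervention and post-intervention assessments using a t-test to test the primary hypothesis". The text gives no weights, standard error or degrees of freedom for this test. The primary comparison has no campus stratum; campus appears in a secondary repeat: "We also repeated the test within subgroups defined by school and by covariates".

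The sample-size section gives the layout: "an average of 240 participants per site for surveys", "20 data points, total n = 4,800", with 9 assessments before and 11 after the intervention. Its assumption is "We assigned 60% of the students at baseline to already be a DOD". It reports that the detectable difference "was 4 percentage points for an average change overall (3 campuses") and 7 points within one campus. It says this holds with no drift or a 3-point drift over time before the intervention. It mentions no difference between campuses.

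The design section gives one campus (UHM) three intervention semesters and the other two (UHH, HPU) two each.

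**The concern.** The indicators give each assessment its own level, so the model itself does not confound campus with period. The confounding can arise in the next step, when all pre predictions are set against all post predictions. If one campus supplies a larger share of the post assessments than of the pre assessments, and its students differ in donor status for reasons outside the four adjustment variables, the pre/post difference partly measures campus mix.

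This is the test of the primary hypothesis, used for both donor status and family discussion and repeated in the covariate and propensity strata. The choice of standard error changes the form of the harm but does not remove it. With model standard errors, the bias raises the false-positive rate. With a plain t-test on 20 values, campus differences also inflate the error term and make power depend on the direction of the bias.

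**Working it through.** **Inputs from the documents.** 9 pre and 11 post assessments; 240 surveys each on average (2,160 and 2,640); baseline 60%; two-sided alpha 0.05; power 80%.

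**Assumptions.** The figure with the campus schedule is not shown, so three UHM/UHH/HPU splits are used. Campus ranges of 5 points (62.5/60/57.5%) and 10 points (65/60/55%) are assumed, in both orders.

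**1. The stated figure.** SE = √(0.60×0.40/2160 + 0.64×0.36/2640) = 0.01408. Power at 4 points = Φ(0.04/0.01408 − 1.96) = Φ(0.88) = 81%, and 80% power is reached at 3.94 points. The 4-point figure reproduces. A plain t-test on the 20 values (18 df, sampling error only) gives about 77% power at 4 points and a detectable difference of 4.17. For a single campus, with splits from 2+4 to 4+4 assessments, model standard errors give 6.2-7.5 points and a plain t-test 7.4-10.1; the stated 7 fits the former better.

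**2. Equal weighting cannot be campus-neutral.** Let campus c have a pre and b post assessments. Neutrality requires a/9 = b/11, or 11a = 9b. As 9 and 11 share no factor, a must be 0 or 9, so one campus would hold every assessment. This does not depend on the missing figure.

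**3. Size of the bias.** With m the campus deviation from 60%, bias = Σ m(b/11 − a/9). For pre 2/3/4 and post 5/3/3 at the 10-point range: 5×(5/11 − 2/9) − 5×(3/11 − 4/9) = 5×0.232 + 5×0.172 = 2.02 points.

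**4. Type I error with model standard errors.** SE = √[(0.24/240)(1/9 + 1/11)] = 1.42 points. Type I error = Φ(−1.96 + bias/SE) + Φ(−1.96 − bias/SE). For a bias of 2.02, the ratio is 1.42, giving Φ(−0.54) + Φ(−3.38) = 30%.

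**5. Power of a plain t-test.** From a binomial simulation (40,000 replicates) at a true 4-point effect.

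| Pre / post split | Bias, 5-pt range | Bias, 10-pt range | Type I, model SE, 5 / 10 pt | Plain t-test power, 5-pt range, UHM highest / HPU highest |
|---|---|---|---|---|
| 3/3/3, 4/4/3 | ±0.23 | ±0.45 | 5% / 6% | 68% / 57% |
| 2/3/4, 4/4/3 | ±0.78 | ±1.57 | 9% / 20% | 80% / 43% |
| 2/3/4, 5/3/3 | ±1.01 | ±2.02 | 11% / 30% | 84% / 36% |

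With equal campuses, plain t-test power is 77% for every split.

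**6. A within-campus contrast.** Regress the 20 predictions on campus and pre/post (20 − 3 − 1 = 16 df). In the same simulation the mean estimate is 4.0 for a true 4 points and 0.0 under the null in all of these scenarios. Type I error is about 5%, and power 76%, 74% and 73% for the three splits.

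**7. Why model standard errors alone are not enough.** With equal campuses, no effect and an assumed extra SD of 3 points between assessments (for example from changes in recruitment), a contrast using only model standard errors rejects in about 16% of trials, whether or not it is made within campus. The 16-df contrast stays at 5%.

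**The case against.** The strongest reply is that the plan is silent rather than wrong. A reader might infer that the t-test discards the model's standard errors, but the text does not say so. The longitudinal analysis tests a single predicted percentage against 0, by time and by school, which needs a model standard error, and the 7-point campus figure points the same way. Equal weights are not stated either, and the power section's overall average change could mean an average of campus changes. Nor is this a test on individual students' fitted probabilities: the predictions are made per assessment. These points stand, and they limit the claim to what is unspecified and what follows under equal weighting.

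Second, a reader might infer that campus differences could swamp the effect. The propensity model argues against that: study site was a candidate, fitted on 2,129 pre-intervention surveys, and stepwise selection did not retain it. If those surveys are spread over campuses as in the assumed splits, an unadjusted 2-df site test has 92-94% power for a 10-point range, so that is best read as an upper bound. The power is only 36-39% for a 5-point range. The propensity model also adjusted for college year and tuition source, which the primary model omits, so campus differences carried by those two remain.

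Third, the campus split is assumed, and the mildest one gives little bias. The planned by-school tests are within campus, but they are not the primary test. Finally, having 18 degrees of freedom is not a defect: a t-test on assessment summaries allows for variation between assessments, and a remedy should keep that property.

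**Conclusion.** The concern holds in a limited form. The primary contrast is not stated to be within campus, and equal weighting of 9 pre and 11 post predictions cannot balance three campuses. Under the assumed splits, the spurious difference is 0.2-1.0 points at a 5-point residual campus range and 0.5-2.0 points at 10 points, in either direction. With model standard errors, type I error is 5-11% and 6-30%. With a plain t-test, power at 4 points is about 36-84% at a 5-point range, against 77% with equal campuses.

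The impossibility of balance follows from the documents. The size rests on the assumed schedule, the assumed campus ranges and 240 surveys per assessment. The lower range is the more credible one, given the stepwise result. The documents do not show that standard errors are ignored or that power is lost outright.

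**What to change.** Make the primary contrast within campus, from the same logistic model and data. Either add campus to the comparison of the 20 predictions (about 16 df), or take each campus's post-minus-pre difference and combine the three by inverse variance. Use a standard error that allows for variation between assessments as well as for repeat surveys by the same student, who can be identified by email address. State the weights and degrees of freedom, and use the same contrast in the covariate and propensity strata.

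The cost is SAP wording and a few lines of code, with no new data. If campuses are in fact equal, power at 4 points falls from 77% to about 73-76%.

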The primary analysis models were repeated in the longitudinal sample, accounting for repeated measures. Further, a logistic model of post-intervention DOD status was performed among the longitudinal sample where the students never reported being a DOD at any pre-intervention assessment. All post repeated measures for these individuals were included in one model (allowing for repeated yes answers) and all post repeated measures up until when the first yes reported for DOD was included in a second model. The independent variables included the assessment indicators, age, sex, ethnicity and religion. The predicted percentage adopting DOD would be obtained from the model and tested against 0 using a t-test. This comparison was repeated for each post-intervention time (e.g., 1st post-test) and for each school, as well as by subgroups defined by covariates. A similar analysis was performed for the "talk to parents" outcome in the subset who never reported having this conversation on any pre-intervention survey.

Lastly, in order to determine if the intervention was more effective in students less likely to be a donor, protocols stratified the statistical analyses using a "propensity score" based on static student characteristics. We anticipated that students with characteristics making them less likely to become a DOD might be more influenced by our intervention. Propensity scores were developed for DOD status by using a logistic regression of DOD status using pre-intervention data to determine predictors from among demographic/sociocultural variables (e.g., age, sex, race, religion, place of birth, years lived in HI, college year, tuition source, college major, college credits, recruitment method, study site and time). The resulting DOD model based on 2129 surveys (Donor: Yes=1137, No=992) included significant factors of age, sex, race, college year, religion, and tuition source, using stepwise variable selection. The resulting logistic regression equation would then be applied to all surveys to obtain predicted probabilities that were used as "propensity scores." The primary analyses for the cross-sectional data set was performed separately for surveys with a low propensity score < 50% and for surveys with a high propensity score ≥ 50%. The analyses for the longitudinal data set were also stratified by low and high pre-intervention propensity scores, based on the average for students who provided ≥ 1 pre-test survey.

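### The adoption models accept a baseline 'no' of any age, so designations and family talks that predate a campus's start can be scored as post-intervention adoption

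*Combined protocol and SAP*

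**What the plan says.** All of the rule is in section 4) Statistical Analyses Protocols.

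- Entry to the longitudinal set: "The longitudinal dataset would include only those students who completed one or more baseline surveys and one or more post-test surveys". One baseline survey, at any time before the campus started, is enough.
- Adoption set: "a logistic model of post-intervention DOD status was performed among the longitudinal sample where the students never reported being a DOD at any pre-intervention assessment".
- What counts: one model uses every post-test answer. For the other, "all post repeated measures up until when the first yes reported for DOD was included in a second model".
- Covariates: "The independent variables included the assessment indicators, age, sex, ethnicity and religion". Time since the last 'no' is not among them.
- Test and reporting: "The predicted percentage adopting DOD would be obtained from the model and tested against 0 using a t-test", and "This comparison was repeated for each post-intervention time (e.g., 1st post-test) and for each school, as well as by subgroups defined by covariates".
- Second outcome: "A similar analysis was performed for the 'talk to parents' outcome in the subset who never reported having this conversation on any pre-intervention survey".

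The two primary-outcome items listed at the start of the document record donor status and whether a family discussion took place. Neither is described as recording a date.

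**The concern.** The adoption percentage is meant to show non-donors becoming donors once their campus was exposed. The rule fixes only that every baseline answer given was 'no' and that a later answer was 'yes'. The event can lie anywhere between the last 'no' and the 'yes', including months before the campus had an intervention.

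Take two HPU students who both answer 'no' in late 2014 and both become donors in mid-2015. One takes a later baseline survey, answers 'yes', and is excluded. The other skips the later baselines, answers 'yes' in May 2016, and is scored as an adopter. Survey attendance, not the timing of the event, decides the classification.

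Because the campuses started at different times, the unexposed time that can be included differs by campus. The percentages are reported by school and by post-test, so a school difference at the first post-test could come partly from older baseline answers.

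**Working it through.** **1. Calendar.** Figure 1 is not shown, so campus starts are inferred. Inputs: surveys November 2014 to December 2016; contests January 2015 to December 2016; three active semesters at UHM and two sequential ones at UHH and HPU; all three sites active in Spring 2016; surveys in "four academic semesters at UHM and UHH and five academic semesters for HPU"; 20 assessments, 9 before and 11 after the intervention.

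UHH and HPU must each include Spring 2016 in two sequential semesters, so the Spring 2015 contests can only be UHM's. Starts at UHM in Spring 2015, UHH in Fall 2015 and HPU in Spring 2016, with end-of-semester surveys throughout and start-of-semester surveys from Fall 2015, give pre/post counts of 1/5, 3/3 and 5/3:

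- pre: 1 + 3 + 5 = 9
- post: 5 + 3 + 3 = 11
- 20 × 240 = 4,800

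All three match the plan. Swapping UHH and HPU under the same survey pattern gives 8/13.

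**2. Longest pre-start gap.** From November 2014 to January 2015, August 2015 and January 2016 is about 2, 9 and 14 months.

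**3. Gap by baseline.** Assumed dates: baselines 1 Dec 2014, 1 May 2015, 24 Aug 2015, 1 Dec 2015, 18 Jan 2016; starts 12 Jan 2015 (UHM), 24 Aug 2015 (UHH), 18 Jan 2016 (HPU). Gap g = days from last 'no' to start / 30.44.

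| Campus | Days | Months | Mean |
|---|---|---|---|
| UHM | 42 | 1.4 | 1.4 |
| UHH | 266, 115, 0 | 8.7, 3.8, 0 | 4.2 |
| HPU | 413, 262, 147, 48, 0 | 13.6, 8.6, 4.8, 1.6, 0 | 5.7 |

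**4. Misplaced adopters.** The documents give no background uptake, so monthly rates r among non-donors are assumed. Share misplaced = 1 − (1 − r)^g, averaged with last baselines spread evenly over a campus's pre-intervention assessments (also assumed). For HPU at 0.5%: (6.57 + 4.22 + 2.39 + 0.79 + 0)/5 = 2.8%.

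| r per month | UHM | UHH | HPU |
|---|---|---|---|
| 0.25% | 0.3% | 1.0% | 1.4% |
| 0.5% | 0.7% | 2.1% | 2.8% |
| 1% | 1.4% | 4.0% | 5.5% |

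The denominator is baseline non-donors.

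**5. Total time from last 'no' to post-test.** The test is against 0, so background uptake after the start counts too. Assumed post-tests: UHM 1 May, 24 Aug and 1 Dec 2015, 18 Jan and 1 May 2016; UHH 1 Dec 2015, 18 Jan and 1 May 2016; HPU 1 May, 22 Aug and 1 Dec 2016. Mean months = (mean gap in days + mean days from start to post-test)/30.44.

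| | UHM | UHH | HPU |
|---|---|---|---|
| First post-test | (42 + 109)/30.44 = 5.0 | (127 + 99)/30.44 = 7.4 | (174 + 104)/30.44 = 9.1 |
| All post-tests | (42 + 300.4)/30.44 = 11.2 | (127 + 165.7)/30.44 = 9.6 | (174 + 213)/30.44 = 12.7 |

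The gradient from UHM to HPU is present at the first post-test and absent when post-tests are pooled.

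**6. Effect of requiring a 'no' at the final pre-intervention assessment.** The gap falls to 1.4, 0 and 0 months.

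- First post-test: 151/30.44 = 5.0, 99/30.44 = 3.3 and 104/30.44 = 3.4 months. The range narrows from about 4.2 to 1.7.
- Pooled: 11.2, 5.4 and 7.0 months. The range widens from 12.7 − 9.6 = 3.1 to 11.2 − 5.4 = 5.8.

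**The case against.** **The schedule is inferred.** Surveys at the beginning and end of 4 + 4 + 5 = 13 semesters would be 26 assessments, not 20; the calendar above reaches 20 only by leaving out some start-of-semester rounds. A calendar with UHH starting last is not strictly excluded and would move the worst case to UHH. This stands. It changes which campus is most affected, not the gap in the rule.

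**The long gaps may be rare.** The 14-month case needs an HPU student to skip four later baselines. Agreeing respondents were emailed about surveys later in the same semester, and current enrollment was checked each time; both plausibly favour recent answers. This stands too: the number misclassified is unknown, and the even spread is only an illustration.

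**The real fault is the test against 0.** With no comparator, background adoption counts as effect whether it falls before or after the start. That is a separate weakness and the restriction does not cure it. But a comparator would not by itself take pre-start events out of the numerator, so the definition still needs correcting.

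**School rankings.** A reader might infer that every per-school percentage is inflated least at UHM and most at HPU. The pooled times of 11.2, 9.6 and 12.7 months do not support that, because UHM's longer follow-up offsets its short gap.

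**Comparison with the detectable difference.** A reader might also set these percentages beside the plan's 7-point single-campus figure. That figure is a prevalence difference among all students. Non-donors are about 40% (60% assumed donors at baseline) to 47% (992/2129) of students, so HPU's 1.4-5.5% is roughly 1.4 × 0.40 = 0.6 to 5.5 × 0.466 = 2.6 prevalence points.

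**Conclusion.** The point holds for the longitudinal adoption models of both outcomes. Followed literally, the rule scores some pre-start designations and family talks as post-intervention adoption, and nothing elsewhere in the document prevents it.

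The possible pre-start gap is about 1-2 months at UHM, 9 at UHH and 14 at HPU. These are maxima on an inferred calendar that reproduces the stated 9/11 split. The average misplaced share, from 0.3% at UHM under the lowest assumed rate to 5.5% at HPU under the highest, rests on assumed dates, background rates and an even spread of last baselines. Unequal inflation across campuses is shown for pre-start time and the first post-test only.

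The documents do not support extending this to the main result. The primary cross-sectional comparison of pre- and post-intervention assessments does not use the adoption set and is unaffected.

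**What to change.** In the longitudinal paragraph of section 4) Statistical Analyses Protocols, for both outcomes:

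1. Define the adoption set as students who answered 'no' at every baseline survey they took and whose last 'no' was at their campus's final pre-intervention assessment.
2. Report adoption by school at matched post-tests, such as the first, and show the months from last 'no' to post-test beside each figure. Do not rank schools on percentages pooled over post-tests, because follow-up length differs by campus.
3. Keep the present all-baselines set as a sensitivity analysis. Do not give a UHM figure predicted at a zero-month gap: on the inferred schedule UHM has one baseline, so its gap does not vary and the slope would have to come from the other campuses.
4. State that the restriction removes pre-start events only (about 1.4 months would remain at UHM) and does not supply a comparator for the test against 0.

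The cost is a wording change and a re-run on data already collected: each survey belongs to a known assessment point, and repeat respondents are identifiable by email address. The downside is fewer students in the adoption set at UHH and HPU, hence wider intervals. On the inferred schedule UHM loses none.

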Design Protocols of eHealth Intervention website: The home page of the website was designed with three main "links" related to Stage of Change and how users felt about organ donation or their reason for coming to the site. For example, the link "I'm uncomfortable" provided information for those who were Precontemplators or might be disgusted

by the thought of OD, while the "I'm interested, need resources" or "I want to win" links provided information for those in the action stage and came to the site for resources or to register for a contest. See Figure 3 on next page:

Figure 3. Website home page

Protocol for Social Media Contests

Along with the iDecide Hawaii website, project accounts / pages on various social media sites including Facebook, Instagram, and a YouTube channel were created. Facebook and Instagram pages were used to announce the contests, and these platforms, along with YouTube, were used to post the winning entries. Links to our social media pages were located atop each page of the project website. RIOs/SAB members were asked to "like" or "follow" our pages and "share" our posts, so they would be seen by their club members. In order to maximize our social media presence, students were asked to post their picture/video entries on their personal accounts and include our project hashtag (e.g., #idecidehawaiiphoto). This allowed their "followers" to see the video/picture and to be connected to others' entries from the current and previous contests by simply clicking the hashtag.

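### The longitudinal plan sets a one-way adoption rate against zero and gives no matching loss rate among baseline donors, so a significant adoption result can coexist with no net gain

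*Combined protocol and SAP*

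**What the plan says.** Section 4, Statistical Analyses Protocols, defines the longitudinal dataset as students with at least one baseline and at least one post-test survey. Baseline donor status plays no part in that definition. Two analyses of DOD status follow.

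1. The primary models are rerun in this sample with allowance for repeated measures. The comparison is of predicted status before and after the intervention, so baseline donors contribute and the result is a net change.
2. A further logistic model of post-intervention status is "performed among the longitudinal sample where the students never reported being a DOD at any pre-intervention assessment". It is fitted twice. The first fit keeps every post-intervention survey from these students, including repeated yes answers. For the other, "all post repeated measures up until when the first yes reported for DOD was included in a second model". The predicted percentage adopting is tested against 0, and the comparison is repeated by post-test time, by school and by covariate subgroup.

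No analysis is described that estimates post-intervention status among students who were donors before the intervention. No count is planned of adopters who later answer no.

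**The concern.** DOD status can move in both directions between surveys, and the plan gives a separate estimate for one direction only. An adoption percentage among people chosen for never having said yes can only be zero or positive. A test against 0 therefore asks whether anyone changed to yes, not whether more students gained the designation than lost it. Because status is self-reported, inconsistent answering alone would also appear as adoption in a group selected in this way. The yes-to-no rate is the natural check on that.

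What is at stake is how a positive adoption result is read. Without the reverse flow beside it, a reader may take it as evidence of benefit when the same data show little or no net change. A small net effect would also be reported without saying directly whether few students changed or whether gains and losses offset each other.

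**Working it through.** **The plan's own figure.** From the sample size section: "We assigned 60% of the students at baseline to already be a DOD"; "resulting in an average of 240 participants per site for surveys"; "20 data points, total n = 4,800"; "comparing the 9 pre- and 11 post- intervention assessments"; two-sided alpha 0.05; 80% power; stated minimum detectable difference (MDD) 4 points overall.

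- Surveys: 9 × 240 = 2,160 before and 11 × 240 = 2,640 after, 4,800 in all.
- 60% v 64%, two-proportion test. Pooled proportion 0.622; standard error under the null √[0.622 × 0.378 × (1/2,160 + 1/2,640)] = 0.01407; under the alternative √[0.60 × 0.40/2,160 + 0.64 × 0.36/2,640] = 0.01409. Power = Φ[(0.04 − 1.96 × 0.01407)/0.01409] = 81.1%. Solving for 80% power gives an MDD of 3.94 points, so the stated 4 reproduces.
- A cross-check simulated an unpaired t-test on the 20 point prevalences, without drift or covariates. It gave 76.5% power at 4 points and 92.0% at 5.
- 60% v 56% by the same two-proportion formula: power 79.8%. The pre/post comparison can therefore detect a net fall about as well as a net rise. This holds for the full survey set; the longitudinal n is not given.

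**Gains and losses.** From the propensity-score paragraph of section 4: 1,137 yes and 992 no among 2,129 pre-intervention surveys.

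- Donor share d = 1,137/2,129 = 53.4%; non-donor share 1 − d = 46.6%.
- Net change = a(1 − d) − l·d, where a is adoption among non-donors and l is loss among donors. Both are assumptions.
- a = 10%: gain 0.10 × 46.6 = 4.66 points. With l = 5%: loss 0.05 × 53.4 = 2.67 points, net +1.99. Net is zero at l = 4.66/53.4 = 8.7%.
- The adoption estimate is 10% whether l is 0, 5% or 8.7%, while the net moves from +4.66 to +1.99 to 0.

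Cancelling loss, l = a(1 − d)/d:

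| Assumed adoption | Cancelling loss, d = 53.4% | Cancelling loss, d = 60% |
|---|---|---|
| 5% | 4.4% | 3.3% |
| 10% | 8.7% | 6.7% |
| 15% | 13.1% | 10.0% |
| 20% | 17.4% | 13.3% |

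**How often the test against 0 rejects when net change is exactly zero.** Simulation, 5,000 runs per cell, d = 60%, adoption set to balance loss (2% × 60% = 3% × 40% = 1.2 points; 5% × 60% = 7.5% × 40% = 3.0 points). It uses one post survey per student and a simple binomial z-test at 1.96, as a stand-in for the plan's model-based t-test. The longitudinal n is assumed.

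| Assumed longitudinal n | Non-donors (40%) | 2% loss, 3% adoption | 5% loss, 7.5% adoption |
|---|---|---|---|
| 200 | 80 | 22% | 86% |
| 400 | 160 | 70% | 99.8% |
| 600 | 240 | 93% | 100% |

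The test is doing what it was set up to do, since adoption really is above zero in these runs. The rejections say nothing about net gain.

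**The case against.** A reader might infer that students who give up their designation are never examined, or that such losses cannot be seen at all. The documents do not support that. The rerun of the primary models covers the whole longitudinal sample, so a yes-to-no change lowers the post-intervention prevalence, and a net fall would show there and in the cross-sectional analysis. The first adoption model also keeps surveys after the first yes, so an adopter who later reverts stays in it; only the second model stops there.

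A reader might also take the website design section, which mentions users who could be disgusted "by the thought of OD", as showing that donors were expected to withdraw. It describes an attitude visitors may bring to the site and the content offered to them. It does not describe existing donors reversing, and the documents name no such adverse effect.

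The best remaining argument is that loss can be backed out: l = [a(1 − d) − net]/d. In the example, (4.66 − 1.99)/53.4 = 5.0%. This is fair but only approximate, because the models adjust for covariates, students contribute several surveys, and some have mixed baseline answers. It also gives no confidence interval.

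Finally, the primary hypothesis rests on the pre/post comparison, and the adoption models are additional. That stands, and it limits the point to how the adoption result is reported and read.

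**Conclusion.** The concern holds in a limited form. The plan estimates net change in the longitudinal sample and adoption among students with no pre-intervention yes. It does not estimate loss among baseline donors, and it tests adoption against a value the estimate cannot fall below. A significant adoption result is therefore compatible with no net gain. The illustrative size is an 8.7% loss cancelling 10% adoption, or 4.4% to 17.4% across adoption of 5% to 20%.

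These figures rest on assumed adoption and loss rates, and on a donor split taken from pre-intervention surveys, not from longitudinal students. The 4-point MDD belongs to the 4,800-survey design and should not be used as a yardstick for the longitudinal sample. Nothing here shows that losses occurred, and the primary pre/post test is unaffected. The change is worth making because it alters what a positive adoption result can support, at little cost.

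**What to change.** In the longitudinal part of section 4:

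- Add a pre/post yes/no transition table of DOD status for all longitudinal students, using one baseline rule that partitions the sample: for example the last pre-intervention answer, or never / always / mixed donor before the intervention. The rule matters. If adoption is defined by never having said yes and loss by a yes at the last pre-intervention survey, a student who answered yes and then no before exposure falls in neither group, and the flows do not add up to the net change.
- Report the yes-to-no percentage among baseline donors with a confidence interval, overall and by school, beside adoption and the net change.
- From the first adoption model's data, report how many adopters later answer no.
- State that the test of adoption against 0 does not by itself support a conclusion of benefit, which rests on the net pre/post comparison.

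The cost is one table and a few sentences, with no new data. Precision will be modest. At an assumed 5% loss and 60% donors, the 95% half-width 1.96 × √(0.05 × 0.95/m) is 3.9, 2.8 or 2.3 points for m = 120, 240 or 360 donors (assumed longitudinal n of 200, 400 or 600), and wider by school.
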